5.4.2.3 Criteria for Discontinuation of Nivolumab and Ipililumab

Criteria for discontinuation of both Nivolumab and Ipililumab during the combination therapy period or the Nivolumab alone after no additional Ipililumab is to be given are specified in this section. If a subject meets criteria for discontinuation and the Investigator is unable to determine whether the event is related to both or one study drug, the subject should discontinue both Nivolumab and Ipililumab with the exception of certain cases of liver function test elevation (See Section 5.4.3).

Nivolumab and Ipililumab should both permanently discontinued for any of the following reasons:

- Any Grade 2 drug-related uveitis, eye pain or blurred vision that does not respond to topical therapy and does not improve to Grade 1 severity within the re-treatment period OR requires systemic treatment;
- Grade 3 drug-related uveitis, pneumonitis, bronchospasm, neurologic toxicity, myocarditis, hypersensitivity reaction, or infusion reaction of any duration;
- Any Grade 3 adrenal insufficiency regardless of control with hormone replacement.
- Any Grade 3 drug-related non-skin AE lasting > 7 days or recurs;
- Grade 3 diarrhea or Grade 3 colitis

- Note: Nivolumab alone can be continued if grade 3 colitis or diarrhea lasts ≤ 7 days or if, upon permanent discontinuation of ipililumab, the Principal Investigator approves continued use due to a possible favorable benefit/risk ratio.
- Grade 3 drug-related thrombocytopenia > 7 days or associated with bleeding;
- Grade ≥ 3 drug-related AST**, ALT**, or total bilirubin;
 - ** In most cases of Grade 3 AST or ALT elevation, Nivolumab and Ipililumab will be permanently discontinued. Nivolimab alone or Nivolumab and Ipililumab may be continued with approval from the Principal Investigator if there is a possible favorable benefit/risk ratio.
- Drug-related ALT or AST > 3x ULN in combination with total bilirubin > 2x ULN without reasonable other explanation, indicative of potential DILI, mandates permanent discontinuation of all study drugs;
- Grade 4 drug-related AE or laboratory abnormality (including but not limited to creatinine, AST, ALT, or total bilirubin);
- Any grade meningoencephalitis, myasthenia gravis, or Guillain-Barré syndrome
- Any event that leads to delay in dosing lasting > 12 weeks from the previous dose.

The following scenarios do not require discontinuation of the ipililumab and/or nivolumab:

- Grade 3 drug-related endocrinopathies, adequately controlled with only physiologic hormone replacement;
- Grade 4 neutropenia ≤ 7 days;
- Grade 4 lymphopenia or leukopenia;
- Isolated Grade 4 electrolyte imbalances/abnormalities that are not associated with clinical sequelae and are corrected with supplementation/appropriate management within 72 hours of their onset;
- Grade 4 drug-related endocrinopathy AEs, such as, hyper- or hypothyroidism, or glucose
 intolerance, which resolve or are adequately controlled with physiologic hormone replacement
 (corticosteroids, thyroid hormones) or glucose-controlling agents, respectively, may not require
 discontinuation after discussion with and approval from the Principal Investigator;
- Dosing delays to allow for prolonged steroid tapers to manage drug-related adverse events are allowed. Drug-related adverse events are any toxicity temporally associated with administration of the investigational agent that may be at least possibly related to study treatment;

 Dosing delays lasting > 12 weeks from the previous dose that occur for non-drug-related reasons may be allowed if approved by the Principal Investigator.

Prior to re-initiating treatment in a participant with a dosing delay lasting > 12 weeks, the Principal Investigator must be consulted. Tumor assessments should continue as per protocol even if dosing is delayed. Periodic study visits to assess safety and laboratory studies should also continue as clinically indicated during such dosing delays.

5.4.3 Management of Hepatocellular Toxicity Associated with Cabozantinib and Nivolumab and Ipililumab

Elevations of aminotransferases (ALT and AST) and bilirubin have been observed during treatment with cabozantinib, anti-PD-(L)1 agents, and anti-CTLA-4 agents. It is recommended that subjects with elevation of ALT, AST, and/or bilirubin have more frequent laboratory monitoring of these parameters. If possible, hepatotoxic concomitant medications should be discontinued in subjects who develop increased values of ALT, AST, or bilirubin, and other causes (e.g., cancer-related, infection) should be evaluated.

The following condition requires discontinuation of all study drugs:

 Drug-related ALT or AST > 3x ULN in combination with total bilirubin > 2x ULN without reasonable other explanation, consistent with drug-induced liver injury (DILI).

The table below provides suggested guidance on management of hepatotoxicity related to cabozantinib, Nivolumab and Ipililumab.

In the event cabozantinib is interrupted and Nivolumab and Ipililumab delayed due to a Grade 2 abnormality in a serum transaminase (ALT and/or AST) or serum bilirubin, Nivolumab and (if fewer than 4 ipilulumab doses have been administered and no AE has occurred that led to discontinuation of the ipililumab alone) the ipililumab should be resumed upon return of liver function tests to baseline grade, at which time cabozantinib should be resumed with a dose reduction (from either 40 mg qd to 20 mg qd, or 20 mg qd to 20 mg qod as appropriate).

If no additional ipililimab is to be administered, the dose of cabozantinib may be re escalated no sooner than 10 days after re-initiation of cabozantinib. And then can be further escalated no sooner than 14 days thereafter.

Consult with the Principal Investigator to discuss further management should re-challenge be followed by any recurrence of a Grade 2 or higher liver function test.

Dose delays should not alter the timing of other study assessments, including but not limited to tumor imaging.

For additional information on dose modifications of Nivolumab and Ipililumab, refer to Section 5.4.2 or Appendix A.

Suggested Management of Hepatotoxicity Associated with Study Treatment

Severity of LFT ^a Elevations	Dose Modification Guidance	Management/Follow-up Guidance
AST or ALT $> 1 - \le 3x$ ULN and/or total bili $> 1 - \le 1.5x$ ULN	Cabozantinib: Continue cabozantinib per protocol Nivolimab/Ipilulimab: Continue therapy per protocol	Monitor LFTs per protocol. Discontinue concomitant hepatotoxic medications, if possible.
AST or ALT > 3 - ≤ 5 x ULN or total bili > 1.5 - ≤ 3x ULN	 Cabozantinib: Interrupt cabozantinib dosing. If LFTs return to baseline grade, resume cabozantinib at a reduced dose. After completion of ipililumab, re-escalate cabozantinib dose as per protocol. If no additional ipililumab doses are to be administered, the dose of cabozantinib may be re-escalated no sooner than 10 days after re-initiation of cabozantinib. See above section for additional guidance. Nivolimab/Ipilulimab: Delay therapy per protocol. If LFTs return to baseline grade, resume therapy per protocol. 	 Monitor LFTs twice weekly or more frequently as deemed clinically necessary. If tapering off steroid therapy, monitor LFTs once weekly or more often per clinical judgment^b. If LFTs return to baseline grade, resume with routine monitoring. If LFT elevations persist > 3 days or worsen: Administer 0.5-1 mg/kg/day methylprednisolone or oral equivalent. When LFTs return to baseline grade or CTCAE Grade ≤1, taper steroids over at least 1 month^b. Consider prophylactic antibiotics for opportunistic infections.
AST or ALT > 5x ULN or total bili > 3x ULN or as otherwise specified	 Cabozantinib: Discontinue cabozantinib if ALT or AST > 8x ULN. Otherwise interrupt cabozantinib dosing and resume at a reduced dose after LFTs return to baseline grade (Sponsor approval required) Nivolimab/Ipilulimab: Discontinue therapy for Grade 3 ALT/AST, unless the Investigator in consultation with the Principal Investigator determines a favorable risk/benefit ratio that warrants continuation of both Nivolumab and Ipililumab or of Nivolumab alone 	 Monitor LFTs twice weekly or more frequently as deemed clinically necessary. During steroid taper, monitor LFTs once weekly or more often per clinical judgment^b. For Grade 3: Administer 1.0-2.0 mg/kg/day methylprednisolone IV or IV equivalent. For Grade 4: Administer 2.0 mg/kg/day methylprednisolone IV or IV equivalent. Add prophylactic antibiotics for opportunistic infections. Consult Gastroenterologist. When LFTs return to baseline grade or Grade 2, taper steroids over at least 1 month^b.

		 If LFT elevations do not improve in > 3 days, worsen or rebound: Add mycophenolate mofetil 1g BID. If no response within an additional 3-5 days, consider other immune-suppressants per local guidelines.
ALT or AST > 3x ULN AND total bilirubin > 2x ULN AND no radiographic evidence of biliary obstruction	All study drugs must be discontinued.	Follow the above management/follow-up guidance by grade.

ALT, alanine aminotransferase; AST, aspartate aminotransferase; bili, bilirubin; CTCAE, Common Terminology Criteria for Adverse Events; IV, intravenous; LFT, liver function tests; ULN, upper limit of normal

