5.4.2.1 Dose Delay Criteria for the Nivolumab and Ipililumab

Administration of the Nivolumab and Ipililumab should be delayed, for any of the following:

- Any Grade 2 non-skin, drug-related AE, with the exception of fatigue
- Grade 2 drug-related creatinine, AST, ALT, and/or total bilirubin abnormalities
- Any Grade 3 skin, drug-related AE
- Any Grade 3 drug-related laboratory abnormality, with the following exceptions:
 - Grade 3 lymphopenia does not require dose delay
 - Grade 3 amylase or lipase abnormalities that are not associated with symptoms or clinical manifestations of pancreatitis do not require a dose delay.
 - Grade 3 AST, ALT or total bilirubin may require dose discontinuation. (See Section 5.4.3)
- Grade 4 amylase or lipase value necessitates dose delay for the anti-PD-(L)1 and anti-CTLA-4 and
 abdominal imaging to rule out pancreatitis regardless of presence or absence of symptoms. If the
 diagnostic radiology scan shows no evidence of pancreatitis, the anti-PD-(L)1 and anti-CTLA-4 may
 CONFIDENTIAL Cabozantinib + Nivolimab + Ipililumab Protocol Required Elements

be resumed once the amylase and lipase values return to Grade 3 or lower as long as the subject remains asymptomatic.

 Any AE, laboratory abnormality, or intercurrent illness which, in the judgment of the Investigator, warrants delaying the dose of study medication.

Immuno-oncology agents are associated with AEs that differ in severity and duration from AEs caused by other therapeutic classes. Early recognition and management of AEs associated with immuno-oncology agents may mitigate severe toxicity. Management algorithms or tables (Section 5.4.3 and Appendix A) have been developed to assist investigators in assessing and managing the following groups of AEs:

- Gastrointestinal
- Renal
- Pulmonary
- Hepatic
- Endocrinopathy
- Skin
- Neurological
- Myocarditis
- Infusion-related Reactions

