5.4.2.2 Criteria to Resume Nivolumab and Ipililumab

Delayed doses of Nivolumab and Ipililumab should be administered as soon as the subject meets criteria to resume treatment. If a dose has been delayed, the subject should not wait until the next scheduled dosing date.

Subjects may resume treatment with these study drugs when the drug-related AE(s) resolve to Grade \leq 1 or baseline value, with the following exceptions:

- Subjects may resume treatment in the presence of Grade 2 fatigue.
- Subjects who have not experienced a Grade 3 drug-related skin AE may resume treatment in the presence of Grade 2 skin toxicity.
- Systemic corticosteroids for control of infusion reactions or irAEs must have been tapered to a dose level ≤ 10 mg/day of prednisone equivalent before resuming treatment with Nivolumab and Ipililumab.

- For subjects with AST, ALT, and/or total bilirubin abnormalities, dosing may resume when laboratory values return to baseline grade and corticosteroid therapy has been tapered to no higher than the equivalent of 10 mg of prednisone per day.
 - Note: Drug-related ALT or AST > 3x ULN in combination with total bilirubin > 2x ULN without reasonable other explanation, consistent with DILI mandates permanent discontinuation of all study drugs.

Note: Nivolumab and Ipililumab, or Ipililumab alone, may be continued after a Grade 3 ALT or AST has been observed and managed appropriately after a positive benefit risk ratio has been determined and the Principal Investigator has been consulted (See Section 5.4.3)

- Drug-related pulmonary toxicity, diarrhea, or colitis must have resolved to baseline before
 treatment is resumed. Subjects with persistent Grade 1 pneumonitis after completion of a steroid
 taper over at least 1 month may be eligible for retreatment if discussed with and approved by the
 Principal Investigator.
- Drug-related endocrinopathies adequately controlled with only physiologic hormone replacement may resume treatment.
- If all study treatment is interrupted for > 12 weeks, the subject must be permanently discontinued from study treatment unless approved by the Principal Investigator.

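### Section 5.4.2 gives conflicting instructions, with no order of precedence, on permanently stopping or re-dosing nivolumab and ipilimumab after controlled Grade 3 adrenal insufficiency and after Grade 4 amylase or lipase elevation

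*Combined protocol and SAP*

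**What the plan says.** Section 5.4.2.3 opens its stop list with "Nivolumab and Ipililumab should both permanently discontinued for any of the following reasons". Two entries matter here:

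- "Any Grade 3 adrenal insufficiency regardless of control with hormone replacement"
- "Grade 4 drug-related AE or laboratory abnormality", followed by a parenthesis that names creatinine, AST, ALT and total bilirubin as examples and says that the list is not exhaustive.

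The same section then lists scenarios that do not require discontinuation. One is "Grade 3 drug-related endocrinopathies, adequately controlled with only physiologic hormone replacement". The Grade 4 scenarios are short-lived neutropenia, lymphopenia or leukopenia, isolated electrolyte abnormalities that are corrected promptly, and endocrinopathies that resolve or are controlled. For the last of these, the Principal Investigator must approve continuation. Amylase and lipase are not on the list.

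Section 5.4.2.1 says "Grade 4 amylase or lipase value necessitates dose delay" and requires abdominal imaging. If the scan shows no pancreatitis and the patient remains asymptomatic, both agents may be resumed once the values are Grade 3 or lower.

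Section 5.4.2.2 sets a general resumption threshold of Grade 1 or lower, or baseline, with listed exceptions. One exception is "Drug-related endocrinopathies adequately controlled with only physiologic hormone replacement may resume treatment". None concerns amylase or lipase.

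**The concern.** For each of the two events, one passage orders a permanent stop and another permits treatment to continue or resume. Nothing in Section 5.4.2 says which list governs when both apply.

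The passages carry weight. Section 2.1 makes the conditions in Section 5.4 grounds for required discontinuation. Section 5.4.2.2 says that delayed doses should be given as soon as the resumption criteria are met. Section 14 makes adherence to the treatment plan a monitored item.

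Two things are at stake. A patient may be re-exposed to both agents although a permanent stop is written for that event, or may lose the immunotherapy although another passage allows it to continue. Either outcome also affects the regimen actually delivered, and that regimen is what the PFS and ORR results describe.

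**Working it through.** No arithmetic applies and the plan states no figure to reproduce. The check applies each rule to two defined patients.

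**Patient A:** drug-related Grade 3 adrenal insufficiency, controlled on physiologic hormone replacement only. 
**Patient B:** drug-related Grade 4 amylase or lipase, asymptomatic, no pancreatitis on imaging, value now back to Grade 3.

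| Source | Patient A | Patient B |
|---|---|---|
| 5.4.2.1, delay criteria | No adrenal-specific rule | Delay and image; may now resume |
| 5.4.2.2, resumption criteria | May resume | General threshold (Grade 1 or lower, or baseline) not met; no exception listed |
| 5.4.2.3, stop list | Permanent stop, whatever the hormonal control | Permanent stop, through the Grade 4 laboratory entry |
| 5.4.2.3, exception list | Discontinuation not required | Not listed |

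**Is adrenal insufficiency an endocrinopathy in this protocol?** Yes. The table in Section 7.3 lists it under endocrinopathies, and Section 7.3.1 names the adrenal gland among the endocrine sites. Neither Section 5.4.2.2 nor the exception list carves it out.

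**Does the stop list reach amylase and lipase?** Yes, but only through the open-ended entry "Grade 4 drug-related AE or laboratory abnormality", and only when the value is drug-related. A Grade 4 value that is not drug-related raises no conflict with that entry.

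**Can an ordinary reading rule settle it?** Two are available:

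- *The specific rule governs the general one.* Patient A stops, because the adrenal line is the more specific. Patient B may resume, because the amylase and lipase pathway is the more specific.
- *The exception list overrides the stop list, and only for what it names.* That is how the list works for Grade 4 neutropenia, which would otherwise fall under the Grade 4 entry. Patient A need not stop, because controlled Grade 3 endocrinopathies are named. Patient B stops, because amylase and lipase are not named.

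The two reading rules give opposite answers for both patients, and the protocol adopts neither.

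**A related loose end.** The Grade 4 endocrinopathy exception mentions corticosteroids as a form of physiologic replacement and allows continuation with the Principal Investigator's approval. It could be read as looser than the Grade 3 adrenal rule.

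**The case against.** The strongest reply is that both conflicts come down to drafting. The stop-list line on adrenal insufficiency applies regardless of hormonal control, and that control is the very condition on which other endocrinopathies are exempted. The phrase makes most sense if adrenal insufficiency was meant to fall outside the exemption. Likewise, Section 5.4.2.1 gives a complete pathway for amylase and lipase, while the stop list never names them. Section 5.4.2.2 also governs delayed doses, so a patient who has met a permanent stop may never reach it. These readings are plausible. They do not settle the matter, because no precedence is written and the exception list exists to override the stop list.

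Three stronger readings are tempting, and the documents do not support them.

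- *A reader might infer that an investigator cannot comply with both sets of rules.* The resumption and exception wording is permissive, so stopping the patient breaches none of it. The problem arises for an investigator who uses the permission.
- *A reader might infer that a Grade 4 adrenal case may stay on treatment while a Grade 3 case must stop.* The Grade 4 exception gives thyroid disorders and glucose intolerance as its examples, says only that discontinuation may not be required, and needs approval. The reference to corticosteroids makes the inference arguable, but no rule states it.
- *A reader might infer that sites will diverge, or that these events are expected at a rate that would move PFS or ORR.* The trial is at present single-institution. Section 5.4.1.2 lists raised lipase among laboratory events in at least 5% of cabozantinib-treated subjects, without giving grades. The other sections name event types without rates.

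**Conclusion.** The concern holds in a limited form. For two event types, Section 5.4.2 gives no single instruction on permanent stopping versus re-dosing. The adrenal conflict covers drug-related Grade 3 cases controlled on physiologic hormone replacement. The amylase and lipase conflict covers drug-related Grade 4 values in asymptomatic patients without pancreatitis on imaging. In both, an investigator relying on the permissive passage would re-dose a patient for whom the stop list states a permanent stop.

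The size cannot be put as an expected number of patients, because the documents give no rates at these grades. In a 25-patient trial, each patient handled differently is 1/25 = 4% of the sample. That is a unit of scale, not a forecast, and no effect on PFS or ORR is shown.

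The conclusion rests on the text of Sections 5.4.2.1 to 5.4.2.3 and on the classification of adrenal insufficiency in Sections 7.3 and 7.3.1. The Appendix A endocrinopathy algorithm is a figure that is not shown. It may address adrenal events and could not be checked. The point still merits correction, because it governs re-exposure after a written permanent stop and the correction is cheap.

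**What to change.** Reconcile Sections 5.4.2.1, 5.4.2.2 and both lists in 5.4.2.3 so that each event has one rule.

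- **Adrenal insufficiency:** make the stop list, the exception list and the endocrinopathy line in the resumption criteria agree. State whether the Grade 4 endocrinopathy exception covers adrenal insufficiency.
- **Grade 4 amylase or lipase:** make the delay criteria, the Grade 4 stop entry, the Grade 4 exceptions and the resumption threshold agree.
- **Precedence:** say which list governs when an event appears to fall under both.
- **Appendix A:** check the endocrinopathy algorithm against the reconciled text.

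The medical lead decides which rule stands; this review takes no position on that. The cost is a wording amendment to Section 5.4.2, and to Appendix A if it differs. No new procedures, visits or patients are needed.

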6 CONCOMITANT MEDICATIONS AND THERAPIES

6.1 Allowed Therapy

- Antiemetics and antidiarrheal medications are allowed prophylactically according to standard clinical practice if clinically indicated.
- Granulocyte colony-stimulating factors (G-CSF or GM-CSF) are allowed if used per clinical guidelines (e.g., ASCO or ESMO guidelines).
- Bisphosphonates or RANK-L inhibitors can be used to control bone loss or hypocalcemia if the benefit outweighs the risk per the Investigator's discretion.
 - Note: osteonecrosis of the jaw has been reported in subjects using bisphosphonates (Section 5.4.1.2.9). Oral examinations are recommended at screening to determine eligibility and periodically during the study. In addition, subjects should be advised regarding oral hygiene practice and to quickly report symptoms to the Investigator. Frequent monitoring for potentially overlapping toxicities with study treatment is recommended. Withhold cabozantinib for at least 3 weeks prior to scheduled dental surgery or invasive dental procedures, if possible. Withhold cabozantinib for development of ONJ until complete resolution
- Transfusions and hormone replacement should be utilized as indicated by standard clinical practice.

^a LFTs include AST, ALT and total bilirubin.

^b Subjects on IV steroids may be switched to an equivalent dose of oral corticosteroids (e.g., prednisone) at start of tapering or earlier, once sustained clinical improvement is observed. Lower bioavailability should be taken into account when switching to the equivalent dose of oral corticosteroids.

- Inhaled, intranasal, intra-articular, and topical corticosteroids are allowed if minimal systemic
 absorption. Systemic corticosteroids are allowed for control of infusion reactions or irAEs and
 must be tapered to a dose level ≤ 10 mg/day of prednisone equivalent before next
 administration of the IO agent. Prophylactic steroid treatment for subjects with contrast
 allergies prior to tumor imaging is allowed.
- Individualized anticoagulation therapy with heparin or direct factor Xa inhibitors rivaroxaban, edoxaban, or apixaban is allowed if it can be provided safely and effectively under the following circumstances:
 - At the time of first dose of study treatment:
 - Low dose low molecular weight heparins (LMWH) for prophylactic use are allowed if clinically indicated and the benefit outweighs the risk per the Investigator's discretion.
 - After first dose of study treatment:
 - Low dose low molecular weight heparins (LMWH) for prophylactic use are allowed if clinically indicated and the benefit outweighs the risk per the Investigator's discretion.
 - Accepted clinical guidelines regarding appropriate management while receiving any kind of anticoagulation therapy must be followed. This includes, but is not limited to, subject education regarding the potential adverse drug reactions, monitoring laboratory parameters, dose adjustments (e.g., due to kidney dysfunction). Caution is warranted in settings associated with an increased risk for bleeding such as gastrointestinal cancers, urothelial cancers, gastrointestinal mucosal abnormality (e.g., mucositis), renal or hepatic impairment, thrombocytopenia, arterial hypertension, or prior history of gastrointestinal bleed

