CONFIDENTIAL - Cabozantinib + Nivolimab + Ipililumab Protocol Required Elements

Ipilimumab 1 mg/kg IV			
Day 1 Every 3 weeks	X		
(cycles 1-4)			
Nivolumab 3mg/kg IV			
Day 1 Every 3 weeks	X		
(cycles 1-4)			
Nivolumab 480mg IV		x	
Day 1 every 4 weeks		^	
	Refer to	Refer to	Contrast enhanced CT of the chest,
Disease Assessment	instructions for	instructions	abdomen, pelvis.
Disease Assessificit	interval	for interval	Restaging will occur every 12 weeks (+/-1 week)
Cardiac Assessment	х		ECG/EKG – day 1 of cycles 1-4 only
Specimen Collection or	х	x	Serum for banking (4ml lavender top and
Optional Specimen Banking	^	^	4ml red top)
			(prior to treatment start and on treatment
Biopsy	X		for 10 patients) prestudy and on day 15 for
			consenting patients
Complete Blood Count (CBC)	X*	X	See Clinical Safety Laboratory Assessments.
complete blood count (cbc)	^	^	*Repeat CBC/CMP on D14 of cycles 1-4.
Blood Chemistry	X*	x	See Clinical Safety Laboratory Assessments.
blood Chemistry	^	^	*Repeat CBC/CMP on D14 of cycles 1-4.
			See Clinical Safety Laboratory Assessments.
Thyroid Function Tests	X	X	TSH with reflex to free T4 day 1 of odd
			numbered cycles
Tumor Markers			LDH
Immune Parameters	х	х	Immune parameters assessment. Refer to
			Section 4.4
Study Labs Serum Sample			Please see PK section of the protocol.
Pharmacokinetics (PK)			Section 4.4
Urinalysis UPCR	x	x	UA to evaluate for proteinuria
Pregnancy Test (HCG)	х	х	For WOCBP

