The most frequent AEs experienced by \geq 20% of subjects treated with cabozantinib in descending order of frequency were diarrhea, fatigue, decreased appetite, nausea, palmar-plantar erythodysesthesia syndrome (PPES), vomiting, weight decreased, hypertension, PPES, vomiting, constipation, hypertension, dysgeusia, dysphonia, and asthenia. For a full description of the safety profile of cabozantinib, refer to the cabozantinib Investigator's Brochure.

Subjects may also experience other medically important but less frequent AEs including arterial and venous thrombotic AEs (e.g., deep vein thrombosis [DVT], pulmonary embolism, transient ischemic attack [TIA], and myocardial infarction [MI]), severe hemorrhagic events, proteinuria, wound healing complications, GI perforation, abscesses including intra-abdominal and pelvic abscess, GI and non-GI fistulae formation, osteonecrosis, and RPLS).

Adverse events associated with laboratory abnormalities experienced by ≥ 5% of subjects treated with cabozantinib in descending order of frequency were anemia, AST increased, ALT increased, hypothyroidism, hypokalemia, hypomagnesemia, thrombocytopenia, hypocalcemia, hypophosphatemia, LDH increased, lipase increased, neutropenia, ALP increased, hyponatremia, and leukopenia.

Many AEs can occur early (within the first few weeks) in the course of treatment with cabozantinib, as cabozantinib is expected to reach steady state exposure at approximately 2 weeks following first dose. Events that generally have an early onset include hypocalcemia, hypokalemia, thrombocytopenia, hypertension, PPES, abdominal pain, mucosal inflammation, constipation, diarrhea and vomiting. In addition, earlier onset for events of dehydration was observed in subjects with castrate-resistant prostate cancer (CRPC) when compared with subjects with other tumor types.

Adverse events should be managed with supportive care at the earliest signs of toxicity. Dose reductions and treatment interruptions should be considered. Dose reductions are recommended for events that, if persistent, could become serious or intolerable. Cabozantinib should be discontinued for the following AEs: visceral perforation or fistula formation, severe hemorrhage, serious arterial thromboembolic

events, nephrotic syndrome, hypertensive emergency, persistent uncontrolled hypertension despite optimal medical management, and reversible posterior leukoencephalopathy syndrome (RPLS).

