5.4.1.2.20 Electrolyte Abnormalities

Electrolyte abnormalities, including hypocalcemia, hypokalemia, hypomagnesemia, and hypophosphatemia have been noted in subjects treated with cabozantinib. In some cases these have been Grade 3 or 4 and/or serious. These laboratory values should be evaluated routinely. Deficits should be corrected when an electrolyte abnormality is noted in order to avoid worsening. Correction of electrolyte abnormalities should be accompanied by increased frequency of monitoring.

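### Section 6.1 permits bisphosphonates or RANK-L inhibitors for low calcium, which these drugs lower further and which cabozantinib itself can cause

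*Combined protocol and SAP*

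**What the plan says.** Section 6.1 (Allowed Therapy) includes a bullet stating that "Bisphosphonates or RANK-L inhibitors can be used to control bone loss or hypocalcemia", provided the investigator judges that the benefit exceeds the risk. The note beneath it deals mainly with osteonecrosis of the jaw. It adds that "Frequent monitoring for potentially overlapping toxicities with study treatment is recommended", but does not mention calcium.

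Section 5.4.1.2.20 (Electrolyte Abnormalities) says: "Electrolyte abnormalities, including hypocalcemia, hypokalemia, hypomagnesemia, and hypophosphatemia have been noted in subjects treated with cabozantinib". On severity it says: "In some cases these have been Grade 3 or 4 and/or serious". On management it says: "Deficits should be corrected when an electrolyte abnormality is noted in order to avoid worsening", and "Correction of electrolyte abnormalities should be accompanied by increased frequency of monitoring".

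Section 5.4.1.2, on management of potential cabozantinib adverse events, names hypocalcemia twice. It is in the list of laboratory adverse events seen in at least 5% of cabozantinib-treated subjects. It is also among the early events: "Events that generally have an early onset include hypocalcemia, hypokalemia, thrombocytopenia, hypertension" (the list continues).

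**The concern.** Bisphosphonates and RANK-L inhibitors reduce the release of calcium from bone. They are used for bone loss and for high calcium. They do not raise low calcium and can deepen it. As written, the bullet names low calcium as a reason to give them.

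Low calcium is also an expected laboratory toxicity of cabozantinib, so the situation the bullet describes may well arise. An investigator who followed the permission literally would give a calcium-lowering drug to a patient whose calcium is already low, when another section asks for the deficit to be corrected. Two further parts of the protocol add to this:

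- Section 5.4.1.2.9 lists bisphosphonates and denosumab as added risk factors for osteonecrosis. A patient treated for low calcium would take on that risk with no benefit for that indication.
- Section 5.4.1.2.16 includes calcium among the electrolytes to check and correct when the QTcF interval is prolonged, so low calcium also matters for cardiac safety in this trial.

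**Working it through.** The plan states no figure that depends on this wording, so there is nothing to reproduce. The check compares the relevant sections, then looks at how far routine monitoring limits the consequence.

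**Step 1: how the word is used.** In the available text, hypocalcemia occurs as follows.

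| Place | Occurrences | Role |
|---|---|---|
| Section 5.4.1.2 | 2 | laboratory adverse event; early-onset event |
| Section 5.4.1.2.20 | 1 | cabozantinib toxicity to be corrected |
| Section 6.1 | 1 | reason to give a bisphosphonate or RANK-L inhibitor |

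The total is 2 + 1 + 1 = 4. Three uses describe harm from the study drug and one describes an indication. Hypercalcemia occurs 0 times, so nothing elsewhere shows that the opposite word was meant. The figures in Appendix A could not be read and are not covered by this count.

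**Step 2: direction.** Section 5.4.1.2.20 requires action that raises calcium. The drugs permitted in Section 6.1 lower it. The two sections conflict only when this pharmacological fact is added, since the documents do not state it. The fact is a basic property of both classes and does not rest on any particular source.

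**Step 3: is the text in force?** The bullet is in the current allowed-therapy list. The sentence is complete and grammatical, which gives no reason to suspect a text-extraction fault.

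**Step 4: how soon would routine tests show a fall?** Calcium is in the chemistry panel of Section 4.1.1. The Section 4.2 table schedules chemistry on Day 1 of every cycle, with the instruction "Repeat CBC/CMP on D14 of cycles 1-4". Assume that the Day 14 metabolic panel includes calcium.

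- Cycles 1-4 (21 days each): draws on study days 1, 14, 22, 35, 43, 56, 64 and 77, which is 4 × 2 = 8 draws. The gaps are 14 − 1 = 13 days and 22 − 14 = 8 days, repeating.
- Cycle 5 onward (every 4 weeks): draws on days 85, 113, 141 and so on. The gap is 113 − 85 = 28 days. With the ±4-day window at both visits it is at most 28 + 8 = 36 days.
- If both ends of the gaps in cycles 1-4 could also move by 4 days, the limits would be 13 + 8 = 21 and 8 + 8 = 16 days, still shorter than 28.

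These are intervals for a patient with no known abnormality. Once low calcium has been found, Section 5.4.1.2.20 calls for more frequent checks, so the gaps are loose outer bounds and do not measure risk in the patient at issue.

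**Step 5: event rate.** None can be given. The documents do not say how many patients would receive these drugs for low calcium.

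**The case against.** The strongest reply is that the protocol already contains the risk. The bullet permits and does not direct. It leaves the decision to the investigator, and most oncologists would recognise the slip. Section 5.4.1.2.20 remains the governing text for low calcium. Section 4.2 allows extra assessments when clinically indicated. On the documents alone the sections do not strictly contradict each other, because the link depends on pharmacology from outside them. The intended word is also an inference, and nothing about the design or analysis changes.

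Most of this stands, and it is why the point is minor. The safeguards make harm unlikely, the routine draw gaps do not quantify the danger, and this is a wording correction with no bearing on the design. Two parts do not carry the objection. That antiresorptive drugs lower calcium is elementary class knowledge, so relying on it is legitimate. And investigator discretion is a weak defence of text that points discretion toward the wrong treatment, particularly as Sections 2 and 8 foresee adding 1-2 sites, whose staff would be new to the protocol.

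**Conclusion.** The concern holds as a minor safety-wording error. Section 6.1 names as an indication a condition that the permitted drugs would worsen and that the study drug can cause, and no other readable part of the protocol corrects it. The likely consequence is small and cannot be expressed as a rate. No endpoint, sample size, power or analysis is touched.

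The conclusion assumes that both drug classes lower serum calcium, which is general pharmacology, and that the unread Appendix A figures do not address the point. That hypercalcemia was the intended word is probable but not certain.

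**What to change.** In the Section 6.1 bullet, replace hypocalcemia with hypercalcemia if the sponsor's clinicians confirm that this was meant. Otherwise delete it as an indication and leave bone loss as the only one. Low calcium would then be managed solely under Section 5.4.1.2.20. A short optional addition would be a calcium check before and during use of these drugs.

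The essential change is one word replaced or two words removed, and it can go into the next routine amendment. It has no effect on design, sample size or analysis.
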